#### Additional Secondary Endpoints:

- Percentage of subjects with  $\geq 30\%$ ,  $\geq 50\%$ , and  $\geq 70\%$  reduction from baseline in Awake Cough Frequency to Day 14 of Treatment Period
- Percentage of Subjects with  $\geq 30\%$ ,  $\geq 50\%$ , and  $\geq 70\%$  reduction from baseline in 24-hour Cough Frequency to Day 14 of Treatment Period
- The number and percentage of subjects with a  $\geq 30\text{mm}$  reduction from baseline to Day 14 of Treatment Period
- The number and percentage of subjects with a  $\geq 1.3$  point increase from baseline to Day 14 of Treatment Period

## 4. STUDY DESIGN

ADX-629-CC-001 is a Phase 2, multicenter, randomized, double-blind, placebo-controlled, two-period crossover trial to evaluate the safety, tolerability, and efficacy of ADX-629 300 mg administered orally BID for 14 days to approximately 50 adult subjects with refractory or unexplained chronic cough.

Subjects will be screened over a period of up to 3 weeks. Eligible subjects will be randomized to one of two treatment sequences. Subjects in one sequence will receive ADX-629 in Treatment Period 1 and matching-placebo in Treatment Period 2, while subjects in the other sequence will receive the matching placebo in Treatment Period 1 and ADX-629 in Treatment Period 2.

[figure not shown]
Subjects will receive their allocated treatment for 2 weeks within each treatment period. Each subject will have a washout period of 2 weeks  $\pm$  2 days between the two trial periods and will undergo a follow-up assessment approximately 1 to 2 weeks after the last dose of trial treatment. Subjects will be required to attend visits for screening and at the start and end of each treatment period. Each visit will require the subject to attend the clinic or to be visited by research staff on consecutive days. At Screening (Visit 1) and on Days 0 (Visit 2 and Visit 6) and 13 (Visit 4 and Visit 8) of each treatment period, the subject will be fitted with a cough recorder to collect cough count data over a period of 24 hours. The cough recorder will be removed the next day once the 24-hour recording has been completed. The trial will include 5 cough recorder sessions in total.

The trial duration for each subject will be up to 11 weeks as follows: up to 3 weeks for screening, 2 weeks for each treatment period, a 2-week washout between treatment periods, and a 2-week follow-up period.

Should a subject discontinue trial treatment, they will be requested to participate in an early (ET) termination visit as soon as possible after the subject stops taking trial treatment. The subjects should have their follow-up visit 1 to 2 weeks after their last dose of trial treatment; however, if their ET visit is more than 1 week after their last dose, they will not be required to have a follow-up safety assessment.

The follow-up safety assessment will be conducted as an in-clinic visit for follow-up laboratory parameters, vital signs, or electrocardiogram (ECG) parameters.

The trial design is illustrated in Figure 1.

**Figure 1: Schematic of Trial Design**

[figure not shown]
Abbreviation: BID=twice daily.

a Subjects will attend the clinic or be visited by research staff on consecutive days. The cough recorder will be fitted at Screening, on Day 0, and on Day 13 of each treatment period to enable cough count data recording over a period of 24 hours.

[figure not shown]
[figure not shown]
#### **4.1 Summary of the Schedule of Assessments**

[figure not shown]
[figure not shown]
A summary of the trial assessment schedule is provided in Table 1.

**Table 1: Schedule of Assessments**

The content of Table 1 is completely redacted with a large black rectangle.

## 5. DETERMINATION OF SAMPLE SIZE

The power is increased to over 90% for treatment improvements greater than 35%. By allowing for a reduction in power due to subject withdrawals, approximately 50 subjects will be randomized.

The null ( $H_0$ ) and alternative ( $H_1$ ) hypotheses for the key secondary efficacy endpoint (awake cough frequency) can be expressed as:

$$H_0: \mu_{ADX} = \mu_{PLA}$$

$$H_1: \mu_{ADX} \neq \mu_{PLA}$$

where  $\mu_{ADX}$  and  $\mu_{PLA}$  are the mean changes from baseline in cough frequency for ADX-629 and placebo respectively.

## 6. MULTICENTER CLINICAL TRIAL

This trial is a multicenter study, with approximately 15 centers participating. Approximately 50 subjects will be randomly assigned, leading to approximately 3 to 5 subjects for each center. The expected low number of subjects at some centers does not allow the center to be included as a covariate in the statistical model. Since there will be centers with few subjects, the inclusion of those centers as covariates in the statistical model is not meaningful. Furthermore, pooling these centers to form one center of a size comparable to other centers has little or no scientific justification. Also, randomization was not stratified by center.

## 7. INTERIM ANALYSIS AND DATA MONITORING

No interim analysis is planned for this study.

## 8. GENERAL ANALYSIS CONSIDERATIONS

The statistical analyses will be reported using summary tables, listings, and figures (TLFs). The International Council for Harmonisation of Technical Requirements for Pharmaceuticals for Human Use (ICH) numbering convention will be used for all TLFs.

Unless otherwise noted, all statistical testing will be 2-sided and performed at the 0.05 significance level. Tests will be declared statistically significant if the calculated  $P$ -value is  $\leq 0.05$ .

Continuous variables will be summarized by presenting the number of observations, means, standard deviations (SDs), medians, minimums, and maximums.

Categorical variables will be summarized by presenting counts and percentages of subjects in corresponding categories. All possible categories defined in the CRF will be populated, even with zero counts. Percentages for missing values are omitted and do not account for the percent calculation of other categories. Percentages are based on the total category count, excluding the missing category if not otherwise mentioned. The total number of subjects is used as the denominator in certain tables (e.g., adverse events [AEs]). Footnotes will specify the percent basis in those cases.

Baseline summaries will be presented by treatment sequence and include a total summary column.

Individual subject data obtained from the eCRFs, external vendors, central clinical laboratory, central ECG laboratory, and any derived data will be presented by subject in data listings.

The version of the WHODrug and Medical Dictionary for Regulatory Activities (MedDRA) coding dictionaries used for coding of concomitant medications and medical histories, respectively, will be specified in the final Medical Coding Plan.

After all the data have been verified, coded if necessary, and entered into the database, a review will be performed.

The analyses described in this plan are considered a priori in that they have been defined before breaking the blind.

Any analyses performed after breaking the blind will be considered post hoc and exploratory. Post hoc analyses will be labeled as such on the output and identified in the CSR.

All analyses and tabulations will be performed using SAS® statistical software, version 9.4 or higher (SAS Institute Inc). Tables, listings, and figures will be presented in RTF format.

The process for SAS program validation and quality control (QC) for programs and outputs is documented in the Synteract working instruction "SAS Programming Quality Control." Study-specific QC requirements can be found in APPENDIX B: SAS PROGRAMMING QUALITY CONTROL REQUIREMENTS.

## 8.1 Baseline Values

For this crossover study, 2 types of baseline will be defined as follows:

- The study baseline is defined as the most recent non-missing measurement(s), either scheduled or unscheduled, collected prior to the first dose of study drug in the study. Study baseline may include measurements from Visit 1 (Screening) to Visit 2, prior to the first dose in Treatment Period 1.
- The treatment period baseline is defined as the most recent non-missing measurement(s), either scheduled or unscheduled, collected before the first dose of study drug in each Treatment Period. For Treatment Period 1, baseline may include measurements from Visit 1 (Screening) to Visit 2, prior to the first dose in Treatment Period 1. For Treatment Period 2, the period baseline may include any measurement that occurs after the end of the wash-out period and prior to the first dose at Visit 7 in Treatment Period 2.

Unscheduled visits, repeat measurements, and averages may be used in the determination of baseline values, when applicable.

## 8.2 Handling of Missing Data

No imputations will be made for missing values. Summaries will be based on observed data only.

## 8.3 Early Withdrawal Assessments

Early withdrawal assessments of efficacy parameters; cough severity, Leicester Cough Questionnaire (LCQ), Cough Quality of Life Questionnaire (CQLQ), Global Rating of Change, Patient Global Impression of Change (PGIC), and Clinician Global Impression of Change (CGIC), as well as safety laboratory and ECG assessments, will be analyzed with the Day 14 assessments of the relevant withdrawal period if treatment is administered for that period. Early withdrawal assessments will be listed as Early Withdrawal.

## 8.4 Unscheduled Visits

Only scheduled post-baseline values will be tabulated. Post-baseline repeat/unscheduled assessments will not be included in the summary statistics. However, these repeat/unscheduled post-baseline assessments will be listed in the relevant appendices to the CSR.

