## 8.3 Assessment of Safety

Safety will be assessed by physical examination and monitoring of AEs, laboratory safety parameters, vital signs, and standard 12-lead ECGs. Unscheduled assessments will be performed if clinically warranted by the Investigator or designee.

CONFIDENTIAL Page 47 of 68

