#### 8.3.3 Clinical Laboratory Analysis

The following clinical laboratory safety assessments will be performed at the times indicated in the schedule of assessments (Table 1).

Safety Laboratory Tests:

- Hematology: hemoglobin, hematocrit, mean corpuscular volume (MCV), mean corpuscular hemoglobin (MCH), mean corpuscular hemoglobin concentration (MCHC), red blood cell (RBC) count, white blood cell count with differential (neutrophils, lymphocytes, monocytes, eosinophils, and basophils), and platelet count.
- Serum biochemistry: ALT, AST, alkaline phosphatase, gamma-glutamyl transferase, bilirubin (total, direct, and indirect), sodium, potassium, chloride, glucose, blood urea nitrogen, creatinine, albumin, amylase, uric acid, creatine kinase, calcium, magnesium, bicarbonate, lactate dehydrogenase, triglycerides, HDL cholesterol, and low-density lipoprotein cholesterol, and eGFR/1.73 m^2 CKD-EPI.

CONFIDENTIAL Page 52 of 68

• Urinalysis: Albumin, creatinine, bilirubin, glucose, ketones, blood, nitrite, pH, protein, specific gravity, and microscopy (if indicated by macroscopic findings). Spot urine protein to creatinine ratio (sUPCR) will also be performed.

*Pregnancy Tests*: Women of childbearing potential will have a serum pregnancy test at screening, and urine pregnancy tests before the first dose at the start of each treatment period (Visit 3 and Visit 7). FSH will be measured at screening only in females thought to be menopausal if pregnancy status is unknown.

Serologies for HIV, Hepatitis B, and Hepatitis C: HIV Ab, HbsAg, HbsAb, and HCV Ab (screening only).

*SARS-CoV-2*: Specimens for SARS-CoV-2 testing will be analyzed centrally.

*Urine Drug Screen*: Tests for amphetamines, barbiturates, benzodiazepines, cannabinoids, cocaine, and opiates.

Cotinine Test: Test for nicotine.

Alcohol breath test: This will be performed locally at screening only.

Instruction on urine and blood sample processing and shipping are available in the laboratory manual.

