## 15.2 Clinical Laboratory Evaluation

Laboratory parameters (serum chemistry, hematology, and urinalysis) will be collected at the following visits:

- Screening (Visit 1),
- Day 1 (Visit 3) and Day 14 (Visit 5) of Treatment Period 1,
- Day 1 (Visit 7) and Day 14 (Visit 9) of Treatment Period 2,
- End of Trial (Visit 10).

*Laboratory Tests:*

- **Hematology:** hemoglobin, hematocrit, mean corpuscular volume, mean corpuscular hemoglobin, mean corpuscular hemoglobin concentration, red blood cell count, white blood cell count with differential (neutrophils, lymphocytes, monocytes, eosinophils, and basophils), and platelet count.
- **Serum Chemistry / Biochemistry:** ALT, AST, alkaline phosphatase, gamma-glutamyl transferase, bilirubin (total, direct, and indirect), sodium, potassium, chloride, glucose, blood urea nitrogen, creatinine, albumin, amylase, uric acid, creatine kinase, calcium, magnesium, bicarbonate, lactate dehydrogenase, triglycerides, HDL cholesterol, and low-density lipoprotein cholesterol, and eGFR/1.73 m^2 CKD-EPI.
- **Urinalysis:** Albumin, creatinine, bilirubin, glucose, ketones, blood, nitrite, pH, protein, specific gravity, and microscopy (if indicated by macroscopic findings).

An evaluation will be done to compare the units for each laboratory test. Where units differ, the units will be converted to a standard unit, and the conversion factors will be provided in analysis data model (ADaM) specifications. The reference ranges can be found in the laboratory manual in Appendix 1 'Protocol Test Summary'. Laboratory values recorded as  $>x$  or  $<x$ , will be analysed as  $x$ .

Laboratory parameters will be summarized by treatment group using descriptive statistics at 'period baseline' and Day 14. Changes from 'period baseline' will also be summarized. For categorical urinalysis results, the number and percentage of subjects in each results category will be presented by treatment group. Here baseline is defined as the pre-dose value on the first day of administration for each period.

Additionally, laboratory parameters will be summarized overall, using descriptive statistics at study baseline and End of Trial, including change from baseline. Here, baseline is defined as the last non-missing measurement (scheduled, unscheduled, or repeat) collected before the first administration of study treatment in the study.

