The categorization into low-normal-high (below lower reference range/ within reference range/ above upper reference range) of each result will also be summarized for each visit, presenting the number and percentage of subjects in each category.

Pregnancy (or follicle-stimulating hormone [FSH] levels), serology, and alcohol breath test results will not be summarized but provided in data listings.

A separate listing of any abnormal laboratory measurements recorded throughout the study will be provided.

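### Scheduled-only safety tables can miss transient abnormalities that do not qualify as adverse events, and sUPCR is missing from the SAP laboratory list

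*SAP*

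**What the plan says.** **Unscheduled values.** SAP 8.4 states "Only scheduled post-baseline values will be tabulated", then "Post-baseline repeat/unscheduled assessments will not be included in the summary statistics", and adds "However, these repeat/unscheduled post-baseline assessments will be listed in the relevant appendices to the CSR". Protocol section 10 has the same rule, so the SAP follows the protocol here. Protocol 8.3 gives the trigger for such tests: "Unscheduled assessments will be performed if clinically warranted by the Investigator or designee".

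**Abnormality tables.** In SAP 15.2 the low/normal/high category "of each result will also be summarized for each visit, presenting the number and percentage of subjects in each category". In SAP 15.5 the ECG interpretation shift table is also per visit. SAP 15.3 plans only descriptive statistics for vital signs at scheduled times. A separate listing covers all abnormal laboratory values.

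**Early withdrawal.** SAP 8.3 analyses early-withdrawal laboratory and ECG values with Day 14. It does not mention vital signs.

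**Adverse events.** Protocol 8.3.1.2 records an abnormal laboratory value or vital sign as an adverse event only if it causes symptoms, needs treatment, leads to discontinuation or meets a seriousness criterion.

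**sUPCR.** Protocol 8.3.3 ends its urinalysis list with "Spot urine protein to creatinine ratio (sUPCR) will also be performed". The SAP 15.2 list has the same parameters, ends at "pH, protein, specific gravity, and microscopy (if indicated by macroscopic findings" and stops there. SAP section 16 reports no changes to the protocol's analyses.

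**The concern.** The primary objective is safety and tolerability, and the primary endpoints include observed values and changes in laboratory, vital-sign and ECG parameters. Tests ordered on clinical grounds between visits are plausibly more likely than routine tests to show something abnormal. Leaving them out of by-visit means is ordinary practice, because they have no common time point. Leaving them out of every count of abnormal subjects is a different matter, because such a count needs no common time point.

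At stake is whether a reader of the tables can see, by treatment, how many subjects had an abnormal value at any time on ADX-629 and on placebo. A listing holds the values but gives no incidence by treatment. For sUPCR the issue is narrower: a parameter measured through the trial, and used as an eligibility limit in Protocol 6.4, has no stated summary.

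**Working it through.** The plan states no figure on this point, so there is none to reproduce. The check is a comparison of the texts, followed by an illustration of scale.

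**Step 1. Scheduled on-treatment looks.** SAP 15.2 and 15.5 place laboratory tests and ECGs on Day 1 and Day 14 of each period. Day 1 is pre-dose and serves as period baseline. That leaves one scheduled on-treatment time per period, Day 14. Vital signs have more: 2 hours after the Day 1 dose, Day 13, and Day 14 before and after dosing. The End of Trial values are summarised overall, not by treatment.

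**Step 2. Trace one finding.** Suppose an unscheduled test on Day 7 shows an abnormal value that has resolved by Day 14.

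| Output | Does the finding appear? |
|---|---|
| By-visit statistics | No (SAP 8.4) |
| Laboratory low/normal/high table | No; Day 14 is correctly shown as normal |
| ECG shift table | No; per visit |
| TEAE tables | Only if recorded as an adverse event |
| Listings | Yes |

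An asymptomatic, untreated, non-serious laboratory or vital-sign abnormality that does not lead to discontinuation therefore enters no by-treatment count. The criteria in Protocol 8.3.1.2 do not name ECG findings.

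**Step 3. Direction.** A subject's worst category over scheduled and unscheduled values is never milder than the worst over scheduled values alone. A scheduled-only count is thus at most equal to the any-time count.

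**Step 4. Scale.** Take n = 50 (SAP section 5) and assume all subjects receive both treatments. One subject is 1/50 = 2.0%. Let u be the share of subjects whose abnormality is seen only at an unscheduled assessment. The documents do not give u, so the values below are assumed. The expected number missed is 50u, and the chance of missing at least one is 1 − (1 − u)^50.

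| u (assumed) | Expected number missed | Chance of at least one |
|---|---|---|
| 1% | 0.5 | 39.5% |
| 2% | 1.0 | 63.6% |
| 5% | 2.5 | 92.3% |
| 10% | 5.0 | 99.5% |

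**Step 5. sUPCR.** Protocol 5.2.2 collects a urine/creatinine ratio at screening, Visits 3, 5, 7, 9 and 10, and early withdrawal. SAP 15.2 lists urine protein and urine creatinine separately. Separate summaries of the two do not give the distribution of each subject's ratio.

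**The case against.** The strongest reply is that the rule is conventional, was set in the protocol, and loses nothing. Much of this stands.

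- The SAP does not depart from the protocol on unscheduled values, and the values remain in listings. With about 50 subjects, those can be read case by case.
- The primary laboratory, vital-sign and ECG endpoint is defined by observed values and changes, not by ever being abnormal. Medically relevant abnormalities reach the TEAE tables whichever visit found them.
- The per-visit tables are not wrong. A normal Day 14 value is normal at Day 14, and the table makes no any-time claim.
- SAP 8.4 also covers repeats. An abnormal scheduled value followed by a normal repeat stays in the table, so the rule does not only remove abnormal results.
- sUPCR is absent from a list and is not excluded by any statement. The table index cannot be seen, and urine protein, serum creatinine and eGFR remain listed.

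A reader might infer an asymmetry, because SAP 8.1 says "Unscheduled visits, repeat measurements, and averages may be used in the determination of baseline values, when applicable" while SAP 8.4 bars such values after baseline. The documents give this little support. For the by-treatment summaries, SAP 15.2, 15.3 and 15.5 define baseline as the pre-dose value on the first day of each period. They name unscheduled values only for the overall study-baseline summaries.

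The reply does not supply a by-treatment any-time count. The adverse-event route is limited to its stated criteria, and the dedicated abnormal-value listing covers laboratory values only.

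**Conclusion.** The point holds as a gap in the planned outputs. Under SAP 8.4 and the tables that can be seen, transient laboratory, vital-sign or ECG abnormalities that do not qualify as adverse events can go uncounted by treatment. The size is unknown. It is 2 percentage points per affected subject out of 50, and the range of 0.5 to 5 subjects rests entirely on assumed shares of 1% to 10%.

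A reader might go further and conclude that the primary safety tables do undercount abnormalities, or that unscheduled tests were taken because something had gone wrong. The documents do not support either. They give no rate of unscheduled tests or of their results, and the stated trigger is only clinical judgement. The TEAE and SAE endpoint is not restricted by SAP 8.4.

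The conclusion assumes that the unseen table index contains no worst-value table. The sUPCR omission is a separate and smaller discrepancy between SAP 15.2 and Protocol 8.3.3, which section 16 does not declare.

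**What to change.** 1. Keep all by-visit statistics on scheduled values.
2. Amend SAP 8.4 to allow one exception: a worst on-treatment (any-time) category or shift table for each of laboratory values, vital signs and ECG. Present it by treatment from period baseline, using scheduled, unscheduled and early-withdrawal values.
3. State the on-treatment window and the categories before unblinding. The laboratory and ECG categories exist in SAP 15.2 and 15.5; the visible text has none for vital signs.
4. Have the new table cover early-withdrawal vital signs, which SAP 8.3 leaves out. Reconcile SAP 8.3 with the footnote in SAP section 9, which marks early withdrawal as listing-only and reassigns it for efficacy tables.
5. Add sUPCR to SAP 15.2, summarised with change from period baseline.

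Protocol section 10 allows additional analyses in the SAP, so no protocol amendment appears necessary. The cost is a few tables from data already collected. Reported abnormality rates would rise slightly, and subjects tested more often have more chances to be counted. A footnote should say so.

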## 9. NOTATION OF TREATMENT GROUPS AND VISITS

### Notation of Treatment Groups

The following notation of treatment groups will be used throughout the report:

Full notation (as used in the study protocol)	Notation used throughout all TLFs
ADX-629 (300 mg tablets)	ADX-629
Placebo	Placebo

### Notation of Treatment sequence

The following notation of treatment groups will be used throughout the report:

Full notation	Notation used throughout all TLFs
Period 1 - ADX-629; Period 2 – Placebo	S1
Period 1 - Placebo; Period 2 – ADX-629	S2

